- 9. Male subjects must be willing to use contraception during the study. With female partners of childbearing potential, male subjects, regardless of their fertility status, must agree to either remain abstinent or use condoms in combination with one additional highly effective method of contraception (e.g., oral or implanted contraceptives, or intrauterine devices) or an effective method of contraception (e.g., diaphragms with spermicide or cervical sponges) during the study and for 14 days after study drug dosing has been completed.
- 10. Fluency in a language of the research site and the utilized assessment materials.

- 11. Has adequate visual and auditory acuity (in the Investigator's judgment) that is sufficient to complete all scheduled assessments (eyeglasses and hearing aids are permitted).
- 12. If receiving background AD medications, including cholinesterase inhibitors, memantine, neuroleptics, anxiolytics, or sleep medications, the dosing regimen must be stable for at least 12 weeks prior to Study Day 1 (randomization) and should be expected to remain stable during the study (Note barbiturates, meprobamate, and high dose benzodiazepines are not allowed, while low dose benzodiazepines, zolpidem, zaleplon and suvorexant are permitted). Chronic medications for conditions other than AD (such as depression) must be prescribed at a stable dose for at least 4 weeks prior to screening. Medications that might have a potential confounding effect on cognitive testing (either prescription or non-prescription medications) should not be modified during the Screening Period (see Section 6.3 for additional details).
- 13. The subject has not been a cigarette smoker or chewed tobacco for at least 3 years (occasional pipe or cigar smoking is permitted, but vaping is not).
- 14. Availability of a person (a study partner) who has frequent and sufficient contact with the study subject (defined as ≥ 10 hours per week), and can:
 - a. provide accurate information regarding the study subject's cognitive and functional abilities in the opinion of the Investigator,
 - b. agree to comply with and participate at all scheduled visits and study procedures,
 - c. sign the necessary consent form,
 - d. maintain the same level of interaction with the study subject throughout the study duration.

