6.1.8. Data Adjustments/Handling/Conventions

All collected data will be presented in listings or Clinical Data Interchange Standards Consortium (CDISC) datasets. Analysis results will be presented and summarized in either tables and/or figures. Data not participant to analysis according to this plan will not appear in any tables or graphs but will be included in the data listings.

All p-values will be displayed in four decimals and rounded using standard scientific notation (e.g., 0.XXXX). If a *p-value* less than 0.0001 occurs, it will be shown in tables as < 0.0001.

The version 24.0 of the Medical Dictionary for Regulatory Activities (MedDRA) will be used to classify all AEs by system organ class (SOC) and preferred term (PT).

Prior and concomitant medications will be classified using Anatomical Therapeutic Chemical class (ATC level 2) and preferred term (ATC level 4) from World Health Organization Drug Dictionary (WHO-DD), WHODrug Global B3 version March2021.

Medications that start before the first dose of study drug are considered prior medications whether or not they were stopped prior to the first dose of study drug. Any medication continuing or starting on or after the first dose of study drug will be considered as concomitant. If a medication starts prior to the first dose of study drug and continues after the first dose of study drug, the medication will be considered as both prior and concomitant.

Adverse events or medications with entirely missing start dates will be classified as treatment-emergent or concomitant, as appropriate.

For partial AE or medication start dates: (a) if only the day is missing, and the month and year match the first dose date and the end date is on or after the first dose date, or AE/medication is ongoing, then the date is assigned the first dose date thus the event/medication will be considered as treatment-emergent/concomitant; if the month and/or year do not match the first dose date or the end date is prior to the first dose date, then the day is assigned the first day of the month (01); (b) if month or the day and month are missing, and the year matches the first dose date and the end date is on or after the first dose date, or AE/medication is ongoing, then the date is assigned the first dose date; if the year does not match the first dose date or the end date is prior to the first dose date, then the day/month are assigned the first day of the year (01JAN).

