7.3. Demographics and Other Baseline Characteristics

All participant demographics and other baseline characteristics will be summarized by randomized treatment group using the ITT analysis set. Demographic and other baseline characteristics will also be summarized for the safety analysis set if it is different from the ITT analysis set.

Demographic and baseline characteristics [age, sex (including child-bearing potential for women), methods of contraception, race, ethnicity, weight, height, body mass index (BMI), and education level] will be summarized using the descriptive statistics. Height and weight will be calculated at screening and then the BMI will be calculated at screening.

Additionally, baseline characteristics including AD family history, Covid-19 infection and vaccination history results, and Apolipoprotein E (ApoE) genotyping will be summarized.

The number and percent of participants reporting medical history, grouped by MedDRA system organ class and preferred term, will be tabulated by randomized treatment group. All medical history data will be presented in a data listing.

Prior medications will be summarized descriptively by treatment group using the number and percentage of participants by Anatomical Therapeutic Chemical class (ATC level 2) and preferred term (ATC level 4). All “Cognitive enhancers” defined by verbatim terms: donepezil (Aricept, Adlarity), galantamine (Razadyne, Reminyl), rivastigmine (Exelon) and memantine (Namenda, Ebixa, Nemdatine) will be summarized separately. All prior medication data will be listed. The cognitive enhancers will be flagged in the prior medication listing.

For the continuous variables, the number of non-missing values and the mean, standard deviation, minimum, median, and maximum will be tabulated.

For the categorical variables, the count and percentage of each value will be tabulated.

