8.4. Subgroup Analyses of Efficacy Variables

The co-primary endpoints and iADRS will be analyzed by baseline severity, with subgroups defined as screening MMSE ≥ 21 and ≤ 27 versus MMSE < 21 . An additional subgroup analysis for the co-primary endpoints and the iADRS will use screening MMSE ≥ 20 and ≤ 27 versus

MMSE < 20. For these analyses, an MMRM model as previously described will be used, except that the model will have additional fixed effects for subgroup and its two-way interactions with treatment and Visit, and the 3-way subgroup-by-treatment-by-Visit interaction; and, baseline scores for the endpoint being analyzed and baseline MMSE and their interactions with Visit will be removed from the model due to their possible confounding with subgroup. Specifically, the analysis will include the categorical, fixed effects of treatment group, subgroup, pooled site, and Visit, along with the two-way interactions of treatment group with Visit and subgroup with Visit, and the three-way treatment group, subgroup, Visit interaction.

Similar models will be used to analyze subgroups by age (defined as < 65, 65-74 or ≥ 75), sex (defined as male or female), ethnicity (categories defined per FDA Guidance), ApoE4 genotype (defined as APOE4 non-carrier, carrier or homozygous) and medication use (cognitive enhancers, defined as yes or no).

There will be two additional subgroup analyses for the NPI-10. The first will include participants with a baseline NPI-10 score ≥ 2. The second will analyze the agitation/aggression domain scores in participants with a non-zero baseline score in that domain.

Note that there will be two sets of results for the mild subgroup. In section 8.2 the mild subgroup analyses are conducted by applying the primary analysis model to the ITT-mild analysis set. Those analyses are the primary means of drawing inference for the mild subgroup. The subgroup analyses described here for the mild / moderate subgroups are the primary means of drawing inference for differential efficacy between the subgroups. The analyses specified in section 8.2 are the primary means of understanding efficacy within the mild subgroup because that approach allows for including the same model as other secondary and primary endpoints.

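### The shared start-date rule in SAP 6.1.8 denies prior status to undated and first-dose-year medications, which misfiles background AD drugs and may blur the baseline cognitive-enhancer subgroup

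*SAP*

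**What the plan says.** SAP 6.1.8 sets the date conventions for adverse events and medications together.

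- **No start date at all:** "Adverse events or medications with entirely missing start dates will be classified as treatment-emergent or concomitant, as appropriate". No date is imputed, and nothing says whether such a medication can also be prior.
- **Day missing, month and year equal to those of first dose, drug ongoing or ended on or after first dose:** "then the date is assigned the first dose date thus the event/medication will be considered as treatment-emergent/concomitant".
- **Month, or day and month, missing:** the trigger is "if month or the day and month are missing, and the year matches the first dose date" together with an end date on or after first dose. The sentence then runs on: "or AE/medication is ongoing, then the date is assigned the first dose date; if the year does not match the first dose date" (or the drug ended before first dose), the start becomes 1 January of the recorded year.
- **Prior status:** "Medications that start before the first dose of study drug are considered prior medications". A drug that starts earlier and continues is both prior and concomitant.

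Protocol 5.2, inclusion criterion 12, says of background AD medication that "the dosing regimen must be stable for at least 12 weeks prior to Study Day 1 (randomization").

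SAP 8.4 plans a subgroup analysis by "medication use (cognitive enhancers, defined as yes or no"). The table list in SAP 13.2 labels it as baseline status for ADAS-Cog12, ADCS-ADL and iADRS. SAP 7.3 and 9.6 identify enhancers by a closed list, "defined by verbatim terms: donepezil (Aricept, Adlarity), galantamine (Razadyne, Reminyl") and so on, although 6.1.8 codes every medication in WHODrug. SAP 13.3 plans one table of enhancers used before first dose (14.3.7.2) and one of enhancers used after it (14.3.7.3).

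**The concern.** Placing an uncertain onset in the treatment period is cautious for an adverse event, because it avoids losing a possible drug effect. For background therapy the same default goes against what eligibility has already established. A participant who meets criterion 12 and is on a cholinesterase inhibitor or memantine at Day 1 must have started it at least 12 weeks earlier, so a Day 1 start cannot be right.

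The misfiled records affect three planned outputs. They can be missing from the prior-medication tables (14.1.2.4.1.1 and 14.1.2.4.1.2) and from Table 14.3.7.2. They can appear in Table 14.3.7.3 without a matching entry in 14.3.7.2, and so read as on-study starts, a change that protocol 6.3 asks the Medical Monitor to review. If baseline enhancer status is built from the prior flag or the imputed date, some users would also sit in the non-user stratum and weaken the contrast that the subgroup analysis is meant to show.

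**Working it through.** The plan states no figure on this point, so the check is to apply the rule to test records.

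**Step 1. Apply 6.1.8 to an ongoing drug.** Assume first dose on 15 Sep 2022. The unbracketed ongoing condition allows two readings:

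- A: the date matches AND (the drug ended on or after first dose OR is ongoing).
- B: (the date matches AND the drug ended on or after first dose) OR is ongoing.

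| Recorded start | Reading A | Reading B |
|---|---|---|
| None | concomitant, no date, prior not provided for | same |
| 2017 | 1 Jan 2017, prior | 15 Sep 2022, not prior |
| 2021 | 1 Jan 2021, prior | 15 Sep 2022, not prior |
| 2022 | 15 Sep 2022, not prior | same |
| Mar 2022 | 1 Mar 2022, prior | 15 Sep 2022, not prior |
| Sep 2022 | 15 Sep 2022, not prior | same |

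Reading B would override, for every ongoing drug, the clause that sends a non-matching year to 1 January. Reading A is therefore the intended one. Under A, prior status is lost only for the undated, first-dose-year and same-month records.

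**Step 2. Compare with inclusion criterion 12.** Twelve weeks is 12 × 7 = 84 days. For first dose on 15 Sep 2022 (day 258 of the year), the latest compatible start is day 258 − 84 = 174, which is 23 Jun 2022. An eligible background AD drug recorded as 2022 is thus placed at least 84 days too late. The same-month branch cannot reach such a drug, because a September start fails the criterion.

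**Step 3. When can the first-dose-year branch apply?** The start must fall in the same calendar year and at least 84 days before first dose. That requires first dose on day 85 (26 March) or later, which is 365 − 84 = 281 of 365 days in a non-leap year. The branch is not confined to a rare calendar window.

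**Step 4. Size.** The documents give neither the prevalence of enhancer use nor the rate of incomplete dates. Let p be the assumed proportion of the 804 randomized participants who use an enhancer, and m the assumed proportion of users with no usable start date on any enhancer record. If status came from the prior flag or imputed date:

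- users moved = 804 × p × m
- share of apparent non-users who are users = pm / (pm + 1 − p)

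With p = 0.40 and m = 0.02: 804 × 0.008 = 6 participants, and 0.008 / 0.608 = 1.3%. With p = 0.80 and m = 0.10: 804 × 0.08 = 64 participants, and 0.08 / 0.28 = 28.6%. A span from trivial to material, resting wholly on assumed inputs, shows that the effect cannot be sized from these documents.

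**The case against.** A reader might infer three stronger claims, and the documents support none of them.

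- **All long-standing drugs with a year-only start become Day 1 starts.** They do not: a start in an earlier year goes to 1 January of that year and stays prior. Nor is an undated drug moved to Day 1; it is classified without a date.
- **Baseline users are counted as non-users.** SAP 8.4 says only yes or no, and nothing ties that status to the prior flag or the imputed date. The affected drugs are still summarized as concomitant enhancers under SAP 9.6. If status is taken from drugs ongoing at baseline, the subgroup is unaffected.
- **An adverse-event rule has been carried over to medications.** The rule is drafted for both. The further conventions at the end of 6.1.8, which push dates past first dose, are expressly limited to adverse-event onset.

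The other side can add that sites must establish 12-week stability and recent discontinuation of these drugs (inclusion criterion 12 and exclusion criteria 29 and 30), so absent timing may be uncommon. The rule does not depend on treatment arm. The subgroup lies outside the testing hierarchy in SAP 6.1.3. A blanket pre-dose default would relabel real on-study starts as background. It is also unproven that the verbatim list would miss any entry.

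All of this limits the scope and importance of the point. It does not remove the mismatch for first-dose-year and undated records, or the missing definition of baseline status. The relabelling argument is sound and shapes the fix.

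**Conclusion.** The point holds in a limited form. As written, an ongoing medication with a year-only start in the first-dose year, or with no start date, does not meet the prior definition. For an eligible user of a background AD drug, that result conflicts with inclusion criterion 12. Misfiling in the prior-medication tables and Table 14.3.7.2 follows directly from the stated rules. Misclassification in the enhancer subgroup of the co-primaries and iADRS is conditional on a derivation that the SAP leaves open.

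The primary conclusions are not at risk. The SAP 8.1 model has no medication term, and the estimand handles concomitant medication by treatment policy. No size can be given. The verdict assumes reading A of the ongoing condition and participants who meet criterion 12. The closed verbatim list is a lesser weakness: coded selection is safer because coding is already planned, but no loss is shown.

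**What to change.** In SAP 6.1.8:

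- Treat a medication recorded at the Screening or Baseline medication review (protocol 7.1.1 and 7.1.3) as prior, and also as concomitant if continuing, when its start is missing or is year-only in the first-dose year, unless the recorded part shows a start on or after first dose.
- Keep the present rule for adverse events and for medications first reported after Day 1.
- Bracket the ongoing condition so that it applies only when the recorded part of the date matches first dose.

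In SAP 8.4, define baseline cognitive-enhancer status as any enhancer ongoing at the Baseline Visit. In SAP 7.3 and 9.6, select enhancers by coded WHODrug term.

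The cost is a few sentences and a small derivation change before database lock. It needs no new assessment, provided the data show at which visit a medication was first recorded, which the documents do not state. The remaining downside is that an occasional on-study start with an uninformative date will be counted as background.

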10. ADVERSE EVENTS/SERIOUS ADVERSE EVENTS

10.1. ADVERSE EVENTS - DEFINITION

An Adverse Event (AE) is any undesirable event that occurs to a subject during a study, whether or not that event is considered related to Study Drug. Monitoring for AEs will start after informed consent has been obtained. Examples include:

- Any treatment-emergent signs and symptoms (events that are marked by a change from the subject's baseline/entry status [e.g., an increase in severity or frequency of pre-existing abnormality or disorder])
- All reactions from Study Drug, an overdose, abuse of drug, withdrawal phenomena, sensitivity or toxicity to Study Drug
- Apparently unrelated illnesses
- Injury or accidents (Note: if a medical condition is known to have caused the injury or accident, the medical condition and the accident should be reported as two separate medical events [e.g., for a fall secondary to dizziness, both "dizziness" and "fall" should be recorded separately])
- Extensions or exacerbations of symptoms, subjective subject-reported events, new clinically significant abnormalities in clinical laboratory, physiological testing or physical examination

All AEs, whether or not related to Study Drug, must be fully documented on the AE page of the CRF and in the subject's clinical chart. Adverse events reported during the screening period or AEs secondary to study-related procedures should always be captured as not having a reasonable possibility the AE was caused by the Study Drug. Unexpected, abnormal laboratory results observed during the Screening Period should be captured as Medical History and not as an AE.

In the event that a subject is withdrawn from the study because of an AE, it must be recorded on the CRF as such. The subject should be followed and treated by the Investigator until the abnormal parameter or symptom has resolved or stabilized.

The Investigator must report all directly observed AEs and all spontaneously reported AEs. The Investigator will ask the subject a non-specific question (e.g., "Have you noticed anything different since your dose of the study medication?") to assess whether any AEs have been experienced since the last assessment. AEs will be identified and documented in the Electronic Data Capture (EDC) system in appropriate medical terminology. The severity and the relationship to the Study Drug will be determined and reported in EDC (see below).

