For partial end dates: (a) if only the day is missing, then the day is assigned the last day of the month; (b) if both day and month are missing, they are assigned the last day of the year (31DEC).

For analysis purposes, repeat laboratory results will not be used unless the original value is indicated as missing or invalid. In such cases, the first non-missing repeat value will be used for data analysis. The international system of units (SI) will be used in reporting all laboratory values.

Participants will be analyzed by the treatment received for all safety and tolerability assessments.

Participants are stratified through the IRT system based upon MMSE score entered. Once an MMSE score is entered, that participant is randomized to either high MMSE (21-27) or low MMSE (16-20) strata. At study start, it was decided to stratify participants in this manner so there would be a balance in the number of participants on placebo vs active drug (and within treatment arms) within each stratum. The stratification of the participants does not impact their probability of being assigned to different treatment arms. Once randomized through IRT, the MMSE score and the stratification assigned cannot be changed.

For instances where the MMSE score was incorrectly entered into IRT, the MMSE score given by the vendor will be used to calculate the strata for safety and efficacy analyses if there are any subgroup analyses.

All collected data will be presented in listings. Data not subject to analysis according to this plan will not appear in any tables or graphs but will be included only in the data listings.

A treatment related AE is any AE with a relationship to the study drug of *“Possibly Related”* or *“Probably Related”* or *“Reasonable Possibility”*.

If partial dates occur, the convention for replacing missing dates for the purpose of statistical analysis is as follows: if just day is missing then the day assigned is the first day of the month or the date of first dose (if in the same month), whichever is later; if just month is missing then the month assigned is the month of the first dose, unless that results in a date before the first dose in which case the month after the first dose is used; and if both month and day are missing then the month assigned is the month of the first dose and the day assigned is either the first day of the month or the first dose date, whichever is later.

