If partial times occur, the convention is as follows: if the missing time occurs on the day of the first dose and both the hour and minute are missing then the time assigned is the time of the first dose, otherwise if both the hour and minute are missing and the date is not the date of first dose the time assigned is 12:00; if the date is the same as the date of the first dose and only hour is missing the hour assigned is 12 or the hour of first dose, whichever is later, and if the date is the same as the date of first dose and only the minute is missing the minute assigned is 30 or the minute of first dose, whichever is later. Otherwise, the hour assigned is 12 if the hour is missing and the date is not the same as the date of first dose and the minute assigned is 30 is the date is not the same as the date of first dose.

These conventions will be applied only to adverse event onset dates and times with the following precaution: if the missing date and time reflect the date and time of onset of an adverse event, the modified date and time will be constructed to match the first documented date/time post drug administration while preserving the order in which the AE was reported in the CRF.

7. Study Participants and Demographics

Participant disposition, demographics and other baseline characteristics, prior medications, and study drug exposure and compliance will be summarized by randomized treatment group and overall, using the ITT analysis set, unless otherwise specified below in each section.

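### SAP 6.1.8 gives two conflicting rules for partial adverse-event onset dates, and one can make an event that ended before first dose treatment-emergent

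*SAP*

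**What the plan says.** **First convention.** An early paragraph of SAP 6.1.8 covers start dates of both AEs and medications: "For partial AE or medication start dates: (a) if only the day is missing", and so on. An event that is ongoing, or that ended on or after first dose, takes the first-dose date if its recorded month and year match (day missing) or its recorded year matches (month, or day and month, missing). Otherwise it takes the start of the recorded month or year. The end date is an explicit test: with the month missing, if "the end date is prior to the first dose date, then the day/month are assigned the first day of the year (01JAN"). The day-missing clause works the same way, using the first of the month.

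**Second convention.** A later paragraph of 6.1.8 starts again. With the day missing, "if just day is missing then the day assigned is the first day of the month or the date of first dose" (when in the same month), whichever is later. With only the month missing, the first-dose month is used, or the following month if that would fall before first dose. With both missing, "if both month and day are missing then the month assigned is the month of the first dose", and the day is the later of the first of that month and the first-dose date. No clause looks at the end date. The closing paragraph of 6.1.8 limits these conventions to AE onset and adds that "the modified date and time will be constructed to match the first documented date/time post drug administration".

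**Where the result is used.** SAP 6.1.4 points to 6.1.8 as a whole and does not rank the two conventions. Under SAP 9.1 a new event is a TEAE if its onset is on or after first dose, and AE summaries are based on TEAEs unless stated otherwise. Protocol v3.0 Section 10.1 says: "Monitoring for AEs will start after informed consent has been obtained".

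**The concern.** The two conventions claim the same data field, partial AE onset, and can give opposite answers. Under the first, a recorded end date before first dose keeps the event out of the TEAE tables. Under the second, the same event can be moved to first dose or later. It is then counted as treatment-emergent although the record shows it was over before any drug was taken, and the dataset holds an onset later than its end.

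Two programmers who both follow the SAP could therefore produce different TEAE counts. The classification feeds the AE tables 14.3.1.1 to 14.3.1.6 and the TEAE-by-renal-function tables 14.5.2.1 and 14.5.2.2.

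**Working it through.** The plan gives no figure for this point, so there is nothing to reproduce. The check applies both conventions as written to the same records and classifies each with the TEAE definition in SAP 9.1.

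**Worked cases.** First dose is assumed to be 20 June 2023. When only the year is recorded, or the month is missing, the recorded year is kept; the second convention does not say which year to use.

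| Recorded onset | End | First convention | Second convention |
|---|---|---|---|
| June 2023, day missing | 15 June 2023 | 1 June 2023, not TEAE | 20 June 2023, TEAE, 5 days after its end |
| 2023 only | 30 May 2023 | 1 January 2023, not TEAE | 20 June 2023, TEAE, 21 days after its end |
| 5th, month missing, 2023 | 15 June 2023 | 1 January 2023, not TEAE | 5 July 2023, TEAE, 20 days after its end |
| May 2023, day missing | 10 June 2023 | 1 May 2023, not TEAE | 1 May 2023, not TEAE |
| June 2023, day missing | ongoing | 20 June 2023, TEAE | 20 June 2023, TEAE |
| 2023 only | 1 August 2023 | 20 June 2023, TEAE | 20 June 2023, TEAE |
| 2024 only | 30 June 2024 | 1 January 2024, TEAE | 1 June 2024, TEAE |

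The first three rows show the conflict. The next three agree. In the last, the dates differ but the classification does not.

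**How often an event that ended before first dose would flip.** Take every first-dose day in 2023, every onset 1 to 60 days earlier (the maximum screening period in Protocol 7.1.1), and every end from onset to the day before first dose. That is 60 × 61 / 2 = 1,830 pairs per first-dose day, and 1,830 × 365 = 667,950 in all. Pairs are weighted equally, which is an assumption.

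- First convention: 0 become TEAEs in every pattern.
- Second convention, day missing: 56,354 / 667,950 = 8.4%.
- Second convention, day and month missing: 594,140 / 667,950 = 88.9%.
- Second convention, month missing: 589,580 / 655,268 = 90.0%, after dropping 12,682 pairs where the rule yields a day that does not exist in the assigned month.

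**Ceiling on affected records.** Screening is at most 60 days and treatment is 52 × 7 = 364 days. If AEs were spread evenly over that time, the pre-dose share would be 60 / (60 + 364) = 14.2%. The documents do not report how often onset dates are partial; take 1-5% as an assumption.

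- Every partial-date pre-dose record misclassified: 14.2% × 1% = 0.14%, and 14.2% × 5% = 0.71%.
- Only the day ever missing: 0.14% × 0.084 = 0.01%, and 0.71% × 0.084 = 0.06%.

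Both ranges still assume a full 60 days of AE collection for everyone and that every pre-dose event ended before dosing. Both are therefore on the high side.

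**The case against.** **Counting uncertain events as treatment-emergent is the conservative choice.** The SAP does this elsewhere: missing severity becomes severe (9.1.1) and missing relationship becomes related (9.1.2). That stands where timing is unknown. A recorded end before first dose settles the timing, and the first convention already accepts this, so the second contradicts the SAP's own choice.

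**The later text might concern only clock times, or its closing clause might resolve the conflict.** Neither reading works. The later paragraph imputes missing days and months, and the closing clause pushes onset past dosing, again without looking at the end date.

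**Few records can be affected.** This stands. Protocol v2.0 began AE monitoring at dosing, and SAP 9.1.2 confirms that some AEs fall under v2.0. Under v3.0, unexpected abnormal screening laboratory results go to medical history. The day-missing clause flips only about 8% of events that ended before first dose; the high shares need the month to be missing for an event at most 60 days old.

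**Nothing inferential depends on it.** This also stands. SAP Section 9 makes the safety analysis descriptive unless otherwise specified, and the rule is identical in both arms. Protocol 10.1 has screening AEs recorded as without a reasonable possibility of drug causation, so drug-related TEAE counts should barely change. All AEs are listed, with non-treatment-emergent ones flagged, although the flag depends on the same imputed date.

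**Conclusion.** The conflict is real and the second convention is wrong as written, but the point is minor: a text correction worth making. It affects only AEs with a partial onset date, a documented end before first dose, and a recorded part compatible with the first-dose month (day missing) or year (month, or day and month, missing). The ceiling is about 0.1-0.7% of AE records, or about 0.01-0.06% if only the day is ever missing. Both ranges rest on the assumed 1-5% partial-date rate. Efficacy is untouched.

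A reader might infer more than the documents support:

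- **That every event that ended before first dose becomes a TEAE.** Complete dates are unaffected, and so is a missing day in a month before the first-dose month.
- **That such records exist.** Collection from consent makes them possible; the documents show none.
- **That one arm is favoured.** The rule does not depend on treatment, so the expected effect is slightly inflated and irreproducible counts in both arms.
- **That wholly missing onset dates are a second contradiction.** SAP 6.1.8 classes such AEs as treatment-emergent with wording that leaves room for judgement. The missing end-date check is a gap to clarify.

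**What to change.** In SAP 6.1.8:

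1. Keep the first convention as the only rule for partial AE onset dates.
2. Delete the later partial-date paragraph, and delete the clause in the closing paragraph that moves onset to after drug administration. Keep wording there that limits the partial-time rule to AE onset times; removing the whole sentence would lose that limit.
3. Add that an AE is not treatment-emergent if its recorded end date, or the latest date that a partial recorded end allows, is before first dose. The latest-date wording matters because 6.1.8 imputes partial end dates to month-end or 31 December. An event with onset and end both recorded only as June, and first dose on 10 June, could have ended as late as 30 June and properly remains a TEAE.
4. As a clarification, apply the same statement when onset is wholly missing.

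The cost is a short SAP text change before unblinding and one date derivation in the safety programs. Data collection and trial conduct do not change.
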